**Part B:**

**For Part B of this study, the actual treatment will be defined as follows:**

- **If a subject receives placebo throughout the Part B of this study, the actual treatment will be defined as placebo**
- **If a subject receives at least one dose of tezepelumab in Part B of this study, the actual treatment will be defined as the highest dose of tezepelumab the subject receives**

Treatment-Emergent Adverse Events

Events categorized as Adverse Events (AEs) including events reported as **Disease Related Events** starting on or after first dose of investigational product as determined by **“Did event start before first dose of investigational product” equal to “No” or missing on the Events eCRF (including either “adverse event” or “disease related event” record on eCRF) and up to End of Study Date.**

Disease Related Events

**Disease-related events are events (serious or non-serious) anticipated to occur in the study population due to the underlying disease as recorded on the Events eCRF page. Details on disease related events can be found in protocol Appendix 4.**

**5.2 Study Dates/Timelines**

End of Study (EOS) Date

The End of Study Date for a **subject** is the date **the subject completes the safety follow-up, or the date of the Early Termination (ET) visit if no safety follow-up is completed. The date the subject has ended the study is recorded on the End of Study Electronic Case Report Form (eCRF).**

Primary Completion Date

The primary completion date is the date when the last subject has completed the assessments for week 16 in Part A of the study.

If the study concludes prior to the primary completion date originally planned in the protocol (ie, early termination of the study), then the primary completion date will be the date when the last subject is assessed or receives an intervention for evaluation in the study (ie, last subject last visit).

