9.1.3 Safety Follow-up

A safety follow-up visit will be conducted 20 weeks after the final dose of study drug (18 weeks after the EOT visit). All subjects who terminate the study early will complete an early termination visit consisting of all assessments included in the EOT (week 52)

visit and these subjects will complete a safety follow-up visit occur 18 weeks after the EOT visit.

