9.1.4 End of Study

The EOS visit will occur 18 weeks after the EOT visit (20 weeks after the final dose of study drug) and is the same as the safety follow-up visit.

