9.2.3.1 Adverse Events

All adverse events observed by the investigator or reported by the subject that occur after the first dose of investigational product through the end of study/safety follow-up visit or 20 weeks after the last administration of investigational product are to be collected/reported.

All adverse events related to any study procedure/activities will be collected/reported after signing the informed consent form through the end of study/safety follow-up visit or 20 weeks after the last dose of investigational product.

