9.2.3.1.1 Time Period and Frequency for Collecting and Reporting Safety Event Information

9.2.3.1.1.1 Disease-related Events

Disease-related events are defined in [Appendix 4](#).

The investigator is responsible for ensuring that all disease-related events observed by the investigator or reported by the subject that occur after the first dose of investigational product(s)/study treatment/protocol-required therapies through the end of study are recorded using the Event CRF.

All serious disease-related events will be recorded and reported to the sponsor or designee within 24 hours. The investigator will submit any updated serious disease-related event data to the sponsor within 24 hours of it being available.

Disease-related events assessed by the investigator to be more severe than expected and/or related to the investigational product(s)/study treatment/protocol-required therapies, and determined to be serious, must be reported on the Event CRF as serious adverse events and recorded and reported per [Appendix 4](#) and [Section 9.2.3.1.1.3](#).

Disease-related events pre-defined for this study include AD.

9.2.3.1.1.2 Adverse Events

The adverse event grading scale to be used for this study will be the Common Terminology Criteria for Adverse Events (CTCAE), version 5.0 and is described in [Appendix 4](#).

The investigator is responsible for ensuring that all adverse events observed by the investigator or reported by the subject that occur after first dose of investigational product(s)/study treatment/protocol-required therapies through the end of study are reported using the Event CRF.

9.2.3.1.1.3 Serious Adverse Events

The investigator is responsible for ensuring that all serious adverse events observed by the investigator or reported by the subject that occur after signing of the informed consent through 20 weeks after the last administration of investigational product are reported using the Event CRF.

All serious adverse events will be collected, recorded and reported to the sponsor or designee within 24 hours, as indicated in [Appendix 4](#). The investigator will submit any updated serious adverse event data to the sponsor within 24 hours of it being available.

The criteria for grade 4 in the CTCAE grading scale differs from the regulatory criteria for serious adverse events. It is left to the investigator's judgment to report these grade 4 abnormalities as serious adverse events.

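### Read literally, the SAP's early-termination fallback for the End of Study Date leaves some serious or fatal events from the protocol's 20-week reporting period out of the safety tables for a narrow group of early leavers

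*SAP*

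**What the plan says.** **SAP.** Section 5.1 defines a treatment-emergent adverse event (TEAE) as one starting on or after the first dose "and up to End of Study Date". Section 5.2 defines that date for a subject as the date the safety follow-up is completed, "or the date of the Early Termination (ET) visit if no safety follow-up is completed". It then adds: "The date the subject has ended the study is recorded on the End of Study Electronic Case Report Form". Section 9.6 runs the whole-study Part A safety analyses from Day 1 to EOS and states no period for Part B. Section 9.6.1 lists the serious and fatal event tables beside the TEAE tables and gives them no longer window.

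**Protocol.** Section 9.2.3.1.1.3 asks for all serious adverse events "after signing of the informed consent through 20 weeks after the last administration of investigational product are reported using the Event CRF". Section 9.2.3.1 asks for adverse events "through the end of study/safety follow-up visit or 20 weeks after the last administration of investigational product are to be collected/reported", while 9.2.3.1.1.2 runs adverse events to the end of study only. On timing, section 9.1.4 states: "The EOS visit will occur 18 weeks after the EOT visit (20 weeks after the final dose of study drug"). Section 9.1.3 and the footnotes to Tables 2-1 and 2-2 give subjects who terminate early an ET visit, then a safety follow-up visit 18 weeks later.

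**The concern.** The SAP ties the end of the safety window to attendance at a visit. The protocol's serious adverse event sentence ties it to time since the last dose. The two agree for anyone who completes the follow-up visit. They part for a subject who has an ET visit and does not reach the follow-up visit, and one reason for not reaching it is the event itself: the subject dies or is too ill to attend. The window then closes retrospectively, before the event that prevented the visit.

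This loss is not random. It would lower serious and fatal event counts among early leavers, and by different amounts across arms if early leaving differs by arm. With about 60 subjects per arm in Part A, one missing death or serious event could matter to an arm comparison. SAP section 10 does not list a shorter safety window among the changes from the protocol, so nothing shows that it was intended.

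**Working it through.** **1. Reproduce the plan's follow-up figures.** From Table 2-2: last dose week 50, EOT week 52, EOS week 70.
- Last dose to EOS: 70 − 50 = 20 weeks.
- EOT to EOS: 70 − 52 = 18 weeks.
- Target days (SAP Appendix A, week × 7 + 1): 351, 365 and 491. So 491 − 351 = 140 days and 491 − 365 = 126 days.

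The protocol's 20 and 18 weeks reproduce exactly.

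**2. Portion of the reporting period cut off by the fallback.** With the ET visit *g* weeks after the last dose and no completed follow-up, the portion after the SAP's date is 20 − *g* weeks. The documents do not fix *g* for early leavers. Taking *g* = 2, as for the scheduled EOT visit, is an assumption, so a range is shown.

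| ET visit after last dose (assumed) | Weeks cut off | Days | Share of 20 weeks |
|---|---|---|---|
| 0 weeks | 20 | 140 | 100% |
| 1 week | 19 | 133 | 95% |
| 2 weeks | 18 | 126 | 90% |
| 4 weeks | 16 | 112 | 80% |

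**3. Apply both rules to one hypothetical Part A subject.** Last dose week 20, ET visit week 22, consent not withdrawn, fatal infection week 30.
- Protocol reporting period ends at week 20 + 20 = 40. The death is reportable.
- The follow-up visit is due at week 22 + 18 = 40 and never happens.
- SAP 5.2 fallback: End of Study Date = week 22.
- SAP 5.1: onset at week 30 is after week 22, so the event is not a TEAE.
- SAP 9.6: Day 1 to EOS also ends at week 22, so the event is outside the whole-study serious and fatal tables.

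If the date on the End of Study eCRF were week 30 (the date of death) and that date governed, the event would be counted. The SAP does not say which date governs.

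**4. Part B.** SAP 9.6 states no period, and 9.6.1 does not label the serious and fatal tables treatment-emergent. The event is lost there only if those tables follow the 5.1 definition.

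**The case against.** **The eCRF date may govern.** Death is a reason for removal from the study (protocol 8.2.2), so the End of Study eCRF could carry the date of death. This stands as a limit: the documents show a fallback rule and unclear precedence, not a certain exclusion. It does not remove the point, because nothing in SAP 5.2 says the recorded date overrides the fallback.

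**The group is small.** This also stands. Subjects who stop treatment are to remain on study (protocol 8.1), so stopping treatment is not early termination. After withdrawal of consent, protocol 8.2 itself limits the data to those up to withdrawal, plus public data where permitted. A subject who dies or is lost without an ET visit has no ET date to fall back on.

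**The protocol is not uniform.** The synopsis gives serious events two alternative end points: the end of study/safety follow-up visit, or 20 weeks after the last dose. For non-serious events, protocol 9.2.3.1.1.2 stops at the end of study, which the SAP follows. The conflict is therefore clear only for serious and fatal events under 9.2.3.1.1.3.

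**Other SAP text.** For non-switchers, the Day 1 to week 16 analysis has a different stop, which can be the end of safety follow-up. That does not alter the EOS bound on the whole-study tables.

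Two stronger readings are tempting and not supported:
- A reader might infer that a subject who attends weeks 52 and 58 but misses week 70 loses the week 58 events. The fallback names only the ET visit, which the protocol reserves for subjects who terminate early. A subject at week 52 on schedule has an EOT visit; the two merely share a table column. For that subject the rule gives no date except the eCRF date.
- A reader might scale the loss by the 10% dropout rate. That rate is a sample-size assumption for the week 16 tests, not a rate of having an ET visit and then no follow-up. The documents give no such rate, and only events actually reported after the ET visit could be dropped.

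**Conclusion.** The point holds for subjects who had an ET visit, did not complete the safety follow-up and did not withdraw consent. For them, the literal SAP rule puts serious or fatal events reported after the ET visit outside the whole-study Part A safety tables, although protocol 9.2.3.1.1.3 requires their reporting through 20 weeks after the last dose. Part B is affected in the same way only if its tables follow SAP 5.1.

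The portion cut off per affected subject is about 18 of 20 weeks if the ET visit is 2 weeks after the last dose, and 16 to 20 weeks if it is 4 to 0 weeks after. Neither the number of subjects nor the number of events can be derived from the documents. The conclusion assumes that the ET fallback, not a later eCRF date, is what gets programmed. If the sponsor intends the eCRF date to govern, one sentence would settle most of it. The efficacy analyses are not touched.

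**What to change.** In the SAP:
- For safety analyses, end the TEAE, serious and fatal event window at the later of (a) the End of Study eCRF date, including date of death, and (b) last IP dose + 140 days (20 × 7). Count all events recorded on the Event CRF within that window.
- Handle data after withdrawal of consent as protocol 8.2 provides.
- Drop the ET-visit fallback in 5.2 for safety purposes, and state how the eCRF date is used.
- Apply the same window to the whole-study Part A tables and to Part B, and state the Part B period in 9.6.

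In the protocol, reconcile the end points of the adverse event sentence (9.2.3.1.1.2) and the serious adverse event sentence (9.2.3.1.1.3).

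The cost is SAP wording and one derivation, since the protocol already requires these events on the Event CRF. The downside is that event collection after the last attended visit is less systematic than at visits; a table footnote should say so.

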### Randomization Date

Randomization Date is defined as the date subject was allocated to a treatment group.

### Study Day

The number of days from Study Day 1, inclusive, given by the following formula:

Study Day = (Date of interest – Date of Study Day 1) + 1, if date of interest is on/after Study Day 1.

Study Day = (Date of interest – Date of Study Day 1), if date of interest is before study day 1.

### Study Day 1

Study day 1 is defined as the first day of IP administration after randomization. If a subject is randomized but never dosed, then set study day 1 to randomization date.

### Switching Date

**If a subject is determined as non-responder at week 16 in Part A as specified by the eCRF, the Switching Date of this subject will be defined as the date that the subject takes the first dose of tezepelumab 420 mg SC Q2W after week 16 in Part A.**

## **5.3 Baseline related definitions**

### Study Baseline

Study baseline is defined as the last non-missing measurement for the endpoint of interest taken **on or before the date of** first dose of investigational product.

**For IGA and EASI, the baseline are the IGA or EASI values collected at “Day 1” visit per protocol schedule of assessment. The values collected at “screening visit” per protocol schedule of assessment could not be used as baseline IGA or EASI.**

### Change from baseline

Change from baseline is defined as (Post-baseline Value – Baseline Value).

### Improvement from baseline

**For endpoints with higher scores reflecting better clinical results, improvement from baseline is defined as (Post-Baseline Value – Baseline Value).**

For endpoints with lower scores as better clinical results, improvement from baseline is defined as (Baseline Value – Post-Baseline Value).

#### Duration of Atopic Dermatitis (years)

The number of years between the date of diagnosis (DXDT) and study Day 1, rounded to one decimal place, is given by formula below to calculate the duration:

Observed portion	Missing portion	Formula to Calculate Duration
Year, Month, Day		$(DAY\ 1 - DXDT + 1)/365.25$
Year, Month	Day	$[Year(DAY\ 1) - Year(DXDT)] + [Month(DAY\ 1) - Month(DXDT)]/12$ *if duration equals 0, add 1 month or 1/12 years (this is to avoid a disease duration of 0)
Year	Month, Day	$[Year(DAY\ 1) - Year(DXDT)]$ *if duration equals 0, add 1 month or 1/12 years (this is to avoid a disease duration of 0)

## 5.4 Study Endpoints

### Investigator's Global Assessment (IGA)

The IGA allows investigators to assess overall disease severity at 1 given time point and consists of a 6-point severity scale from clear to severe disease (0 = clear; 1 = almost clear; 2 = mild disease; 3 = moderate disease; 4 = severe disease; 5 = very severe disease). The IGA uses clinical characteristics of erythema, infiltration, papulation, oozing, and crusting as guidelines for the overall severity assessment ([Breuer et al, 2004](#)).

**For subjects who take rescue medication of TCS/TCI from day 29, their IGA score will be ignored on and after the date of rescue medication.**

### Eczema Area and Severity Index (EASI)

The EASI is designed by modifying the Psoriasis Area and Severity Index, which has been widely used in clinical trials and has been established as a well-accepted and standardized instrument for assessing therapeutic response in patients with psoriasis ([Schmitt et al, 2007](#)). The EASI evaluates 4 natural anatomical regions for severity and extent of key disease signs and focuses on key acute and chronic signs of inflammation (ie, erythema, induration/papulation, excoriation, and lichenification). The maximum score is 72, with higher values indicating more severe disease.

For subjects who take rescue medication of TCS/TCI from day 29, their EASI score will be ignored on and after the date of rescue medication.

Body Region	Severity	Area	Score
Head/Neck (H)	The average degree of severity of each sign (erythema [E], induration/papulation [I], excoriation [EX] and lichenification [L], is defined on a 4-point ordinal scale:  0 = none 1 = mild 2 = moderate 3 = severe	The area is defined on a 7-point ordinal scale:  0 = no eruption 1 = <10% 2 = 10% - 29% 3 = 30% - 49% 4 = 50% - 69% 5 = 70% - 89% 6 = 90% - 100%	$(E+I+EX+L) * Area * 0.1$
Upper Limbs (UL)			$(E+I+EX+L) * Area * 0.2$
Trunk (T)			$(E+I+EX+L) * Area * 0.3$
Lower Limbs (LL)			$(E+I+EX+L) * Area * 0.4$
EASI Score			Sum of scores of H, UL, T, and LL

#### Pruritus NRS via Electronic Diary

The electronic diary includes 1 item to capture subject-reported pruritus. The diary will be completed by the subject at home each morning using an electronic device.

#### EQ-5D-3L

The EuroQoL 5-Dimension Health Questionnaire 3 Level (EQ-5D-3L) is a standardized measure of health status developed by the EuroQol group in order to provide a simple, generic measure of health for clinical and economic appraisal (Greiner 2005). The EQ-5D-3L is a self-administered questionnaire used to assess health status 'today' that is divided into two sections. The first section includes one item addressing each of five dimensions (mobility, self-care, usual activity, pain/discomfort, and anxiety/depression). Each dimension has 3 ordinal levels of severity: "no problem" (1), "some problems" (2), "severe problems" (3). Each item results into a 1-digit number that expresses the level selected for that dimension. The digits for the five dimensions can be combined into a 5-digit number that describes the patient's health state.

In addition, the EQ-5D score will be calculated based on the five attributes on the EQ-5D-3L questionnaire: mobility, self-care, usual activities, pain/discomfort, and anxiety/depression. The answers are recorded as choices of 1, 2, or 3 for each question, with 1 signifying no problem, 2 signifying some problem, and 3 signifying major problem. The calculated EQ-5D score will fall on a scale of 0 to 1, with 0 representing death and 1 representing the perfect health state.

The score will be calculated only if all five attributes are answered. The algorithm for scores starts with everyone having a value of 1, and then points are subtracted from 1 depending on the responses to the five attributes.

If all questions are recorded as 1, the EQ-5D score will stay as 1, nothing will be subtracted. If at least one question is 2 or 3, 0.081 is subtracted. If at least one question is 3, 0.269 is also subtracted. Additional values to be subtracted when the attributes are recorded as 2 or 3 are as follows:

Attribute	Score	
	2	3
Mobility	0.069	0.314
Self-care	0.104	0.214
Usual activity	0.036	0.094
Pain/discomfort	0.123	0.386
Anxiety/depression	0.071	0.236

For example, if a subject recorded mobility as 2, self-care as 3, and the other three items as 1, the EQ-5D score would be  $1 - 0.081 - 0.269 - 0.069 - 0.214 = 0.367$ .

In the second section of the questionnaire, the EQ Visual Analogue Scale (VAS) records the patient's self-rated health on a vertical visual analogue scale where the endpoints are labeled as **100 representing 'Best imaginable health state' and 0 representing 'Worst imaginable health state'**. The VAS can be used as a quantitative measure of health outcome that reflects the patient's own judgment.

For subjects who take rescue medication of TCS/TCI after day 29, their EQ-5D score will be ignored on and after the date of rescue medication.

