##### ***Part A***

For binary endpoints, IGA 0/1, EASI 75, EASI 50/90, each at week 24, week 36 and week 52, the treatment effect will be analyzed using a logistic regression model adjusting for corresponding baseline values as covariates. From each model, odds ratio and 95% CIs will be reported comparing each tezepelumab dose group to placebo.

SCORAD, DLQI, Pruritus NRS, POEM, and PGI-S scores and changes from baseline will be summarized by visit. Absolute improvement and percent improvement will be summarized for the EQ-5D TTO score. In addition, absolute and percent improvement will be calculated for each of the five EQ-5D-3L attributes individually. The EQ VAS score will be summarized.

For continuous endpoints, change from baseline in each of IGA, EASI, SCORAD, Pruritus NRS, PGI-S, POEM, and DLQI at week 24, week 36 and week 52, the treatment effect will be analyzed using the MMRM models with visit and corresponding baseline scores as covariates and an interaction term between arm

and visit. AR(1) variance-covariance structure will be used. Least square means and corresponding 95% CI will be calculated for each treatment group and for the difference between treatment groups. Efficacy data collected after switching to 420 mg SC Q2W point will be truncated.

The MMRM models will be repeated using the Switcher Analysis Set only, utilizing all available observations for subjects in the set. For binary outcomes of IGA 0/1 and EASI 75 at week 24, week 36 and week 52, descriptive summary of response rates will be provided by randomized treatment arm for the Switcher Analysis Set. For continuous outcomes of IGA, EASI, SCORAD, Pruritus NRS, PGI-S, POEM, and DLQI change from Baseline will be summarized descriptively by randomized treatment arm for the Switcher Analysis Set.

Biomarker analysis, if performed, will be detailed in [Section 9.7.4](#).

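### The SAP says the EQ-5D score lies between 0 and 1, but its own algorithm runs from −0.594 to 1, which leaves the planned percent improvement unsound for subjects with a negative or near-zero baseline

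*SAP*

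**What the plan says.** SAP Section 5.4 (EQ-5D-3L) defines one index score built from five items, each coded 1 to 3, and gives its range: "The calculated EQ-5D score will fall on a scale of 0 to 1, with 0 representing death and 1 representing the perfect health state". It then sets out the calculation. "The algorithm for scores starts with everyone having a value of 1, and then points are subtracted from 1", with two overall deductions: "If at least one question is 2 or 3, 0.081 is subtracted" and "If at least one question is 3, 0.269 is also subtracted". A table adds a deduction for each item at level 2 or level 3. A worked example ends at 0.367. No floor or truncation at 0 is mentioned.

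SAP Section 5.3 defines improvement on a scale where higher is better as the post-baseline value minus the baseline value. It gives no percent version.

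SAP Section 9.5.3.1 (Part A) says: "Absolute improvement and percent improvement will be summarized for the EQ-5D TTO score". It plans the same two measures for each of the five items separately. Part B uses the Part A methods for its exploratory endpoints. SAP Section 10 records that the EQ-5D objective was added in the SAP and was not in the protocol.

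**The concern.** Two statements in one section cannot both be true. Either the score is confined to 0 to 1, or it is whatever the deductions produce. The deductions for a subject at level 3 on every item total well over 1, so the calculation goes below zero.

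The contradiction matters because of the percent improvement. On a scale bounded below by 0, dividing a change by its baseline keeps the sign of the change. On a scale that crosses 0 it does not: a negative baseline reverses the sign, and a baseline close to 0 inflates any change without limit. The SAP has no rule for either case. At stake is an exploratory summary in which a marked gain could be shown as a large loss, or in which one value could dominate the mean of a small arm.

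**Working it through.** **Inputs, all from SAP Section 5.4.** Start at 1. Subtract 0.081 if any item is 2 or 3, and a further 0.269 if any item is 3. Item deductions (level 2, then level 3): "Mobility 0.069 0.314"; "Self-care 0.104 0.214"; "Usual activity 0.036 0.094"; pain/discomfort 0.123 and 0.386; anxiety/depression 0.071 and 0.236. States are written as five digits in that order.

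**The plan's own figure.** State 23111: 1 − 0.081 − 0.269 − 0.069 − 0.214 = 0.367. This matches the worked example, so the algorithm is being read as intended.

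**Range.**
- Best state, 11111: nothing is subtracted, so the score is 1.
- Worst state, 33333: the item deductions sum to 0.314 + 0.214 + 0.094 + 0.386 + 0.236 = 1.244. The score is 1 − 0.081 − 0.269 − 1.244 = **−0.594**.

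**How many states are negative.** There are 3^5 = 243 states. Scoring all of them gives 84 below 0 (84/243 = 34.6%). None is exactly 0. The nearest on each side are 33121 at −0.001 and 32222 at 0.002, and 64 states lie within 0.1 of 0.

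**Alternative reading.** If 0.269 replaced 0.081 rather than adding to it, the minimum would be 1 − 0.269 − 1.244 = −0.513 and 58 states would still be negative. That reading also contradicts the worked example. Neither reading yields a range of 0 to 1.

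**Scores used below.**
- 11122: 1 − 0.081 − 0.123 − 0.071 = 0.725
- 11133: 1 − 0.081 − 0.269 − 0.386 − 0.236 = 0.028
- 11233: 0.028 − 0.036 = −0.008
- 22233: −0.008 − 0.069 − 0.104 = −0.181

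**Percent improvement.** The SAP gives no formula. The usual one is assumed: 100 × (post − baseline) / baseline. The last column divides by the absolute value of baseline instead.

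| Baseline | Post | Change | Divided by baseline | Divided by absolute baseline |
|---|---|---|---|---|
| 22233 (−0.181) | 11122 (0.725) | +0.906 | 0.906/−0.181 = −501% | +501% |
| 22233 (−0.181) | 33333 (−0.594) | −0.413 | −0.413/−0.181 = +228% | −228% |
| 11133 (0.028) | 11122 (0.725) | +0.697 | 0.697/0.028 = +2489% | +2489% |
| 11233 (−0.008) | 11122 (0.725) | +0.733 | 0.733/−0.008 = −9162.5% | +9162.5% |

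Rows 1 and 2 show the sign reversing in both directions. Row 3 has a positive baseline, so the choice of denominator makes no difference and the value is still extreme. As an illustration of weight, one subject at +2489% in the 20-subject Part B placebo arm adds 2489/20 ≈ 124 percentage points to the arm mean, if all 20 contribute data.

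**The case against.** The strongest reply is that the problem is narrow. The sign reversal needs a negative baseline and the inflation needs a baseline near zero; elsewhere percent improvement behaves normally. Of the 84 negative states, 83 need at least two items at level 3 and 69 need level 3 on mobility or self-care. Of the remaining 15, 11 need level 3 on both pain/discomfort and anxiety/depression. Exclusion 211 in Protocol Section 6.2 removes subjects with a history or evidence of severe depression, which makes such baselines less likely without ruling them out. This stands as a limit on frequency. It does not make the stated range right or supply the missing rule.

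The sign reversal also rests on an assumed denominator. That is correct, and the last column of the table shows what changes: the sign is repaired and the size is not. Likewise, the label TTO score in Section 9.5.3.1 does not appear in Section 5.4. Treating the two as one score is an inference, though Section 5.4 defines only one EQ-5D score apart from the visual analogue scale.

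Readers would have other information. SAP Sections 9.1 and 9.5 call for medians, quartiles and extremes alongside means, and Section 9.5.3.1 summarises absolute improvement for the same score. The true direction of change would therefore be visible beside a misleading percentage. This stands, and it is why the point is minor.

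Three stronger readings are tempting and should not be drawn:

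- **About a third of subjects are affected.** The 34.6% weights every possible state equally, and nothing in the documents says how subjects are distributed across states.
- **Valid scores will be deleted or truncated to fit 0 to 1.** No passage instructs this. The algorithm is explicit and unfloored, and SAP Section 8.5 keeps outliers that are not data-entry errors.
- **Percent improvement for the single items fails in the same way.** It does not. An item coded 1 to 3 is never zero or negative, so its percent improvement stays between −200% (level 1 to 3) and +67% (level 3 to 1). Whether to report percentages of an ordinal code is a matter of preference.

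**Conclusion.** The range in SAP Section 5.4 is wrong by the section's own rule: it should be −0.594 to 1, with 84 of 243 possible states below 0. This needs no assumption. As a consequence, the percent improvement in Section 9.5.3.1 is not properly defined for subjects whose baseline is negative or close to zero. The size of that second part rests on two assumptions: that the TTO score is the Section 5.4 score, and that the change is divided by baseline. The number of subjects concerned cannot be estimated from the documents.

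The consequence is limited to an exploratory, descriptive output. EQ-5D is not among the endpoints modelled in Section 9.5.3.1 and has no place in the multiplicity procedure of Section 9.5.1.1. Primary and secondary conclusions do not depend on it. This is a correction worth making, not a threat to the trial's findings.

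**What to change.** In SAP Section 5.4, replace the range sentence with one saying that the score runs from −0.594 to 1, that 0 represents death, and that negative values are valid and are not truncated. In Section 9.5.3.1, drop percent improvement for the EQ-5D index score and keep absolute improvement. Because Part B reuses the Part A methods, the one edit covers both parts. Specifying division by the absolute baseline would not be enough, since values near zero would still be extreme.

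Replacing percent improvement for the five single items with shift tables is optional and is not part of this error.

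The cost is two changes of wording and fewer outputs. No new data and no change to any other analysis are needed.
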